## 7.1.2 Overall Survival

Overall Survival (OS): OS is defined as the number of days from date of randomization to the date of death due to any cause. If a patient has not died, the data will be censored at the last date documented to be alive.

## 7.1.3 Progression Free Survival

Progression Free Survival (PFS): PFS is defined as the number of days from date of randomization to the date of earliest disease progression based on Response Assessment in Neuro Oncology (RANO) criteria (as determined by the Investigator) or to the date of death due to any cause, if disease progression does not occur. Patients for whom neither death nor progression have been documented will be censored on the date of the last radiological assessment that the patient was progression-free. If a patient with no post-baseline radiological assessment then the data will be censored at the date of randomization. Patients with two or more missing response assessments prior to a visit with documented disease progression (or death) will be censored at the last visit where the patient was documented to be progression free. Patients who received new anti-cancer therapy or cancer-related surgery prior to progression or death will not be censored at the last assessment where the patient was documented as progression free prior to the new anti-cancer therapy or cancer-related surgery. Detailed censoring rules will be documented in the SAP.

## 7.1.4 Overall Response

The overall response is evaluated at each assessment of the disease according to RANO criteria.

### 7.1.4.1 Best overall response

Best overall response is the best response designation recorded from the date of randomization until disease progression.

### 7.1.4.2 Objective/complete response

Objective/complete response includes best overall responses CR and PR/ CR only. All responses must be confirmed by repeat MRI 4 weeks later.

### 7.1.4.3 Response duration

For responders, duration of objective response (CR/PR) and complete response (CR) will be measured similarly to PFS (see section 7.1.3) but starting from the time measurement criteria for CR/PR or CR (whichever is recorded first) is met

### 7.1.5 Mini Mental State Examination

The Mini Mental State Examination (MMSE): is a brief, standardized tool to grade patients' neurocognitive function. It is an 11-question measure that tests five areas of neurocognitive function: orientation, registration, attention and calculation, recall, and language. The maximum score is 30 which corresponds to the best neurocognitive function. Following Brown *et al.* (Ref. 6), the patient's neurocognitive function will be considered 'impaired' if the MMSE score is 26 or less and 'normal' if it is 27 or more. Since its creation in 1975 by Folstein *et al.* (Ref. 14), the MMSE has been validated and extensively used in both clinical practice and research. Following Tangalos *et al.* (Ref. 45) and as previously used by Brown *et al.*, a decline of more than 3 points in the MMSE score will be considered to represent clinically significant deterioration. See Appendix I. In this study, MMSE will be collected up to progression.

## 7.2 Evaluation of safety

### 7.2.1 Adverse events

All adverse events will be recorded; the investigator will assess whether those events are treatment-related (reasonable possibility, no reasonable possibility) and this assessment will be recorded in the database for all adverse events. A change in grading will be collected by giving an outcome date to the initial AE. A new adverse event needs to be reported to reflect the change in severity.

The collection period will start at baseline i.e. as from 2 weeks before randomization.

All adverse events will be followed until resolution while the patient remains on study treatment. When the patient discontinues study treatment, suspected adverse reactions (AEs for which there is a reasonable possibility that the treatment caused the AE) that started while on study treatment should be followed for 30 days from the date of the last dose of study treatment or until considered chronic/ stable (as judged by the Investigator), whichever comes first.

New SAEs and serious suspected adverse reactions that occur during the 30-day period from the date of the last dose of study treatment administered should be reported and followed until resolved or considered stable / chronic (as judged by the Investigator).

### 7.2.2 General evaluation of adverse events

This study will use the International Common Terminology Criteria for Adverse Events (CTCAE), version 5.0, for adverse event reporting. A copy of the CTCAE can be accessed from the EORTC home page <https://www.eortc.be/services/doc/ctc/>.

*Hematological and biochemistry adverse events will be assessed on the basis of at least monthly blood counts.*

The highest CTCAE grading per cycle and per patient will be computed at the EORTC HQ for analysis.

Planned safety analysis and tabulations are described in the statistics section.

### 7.2.3 Serious adverse events

Serious adverse events are defined by the Good Clinical Practice Guideline.

Serious adverse events should be immediately reported according to the procedure detailed in this protocol (see chapter 16 on Reporting Serious Adverse Events)

### 7.2.4 Toxic deaths

Toxic death is defined as death due to toxicity (defined as adverse events that are not confirmed as unrelated). The cause of death must be reported as "toxicity".

The evaluation of toxic deaths is independent of the evaluation of response (patients can die from toxicity after a complete assessment of the response to therapy).

### **7.2.5 Evaluability for safety**

All patients who have started study treatment will be included in overall safety analyses.

For hematological events, the medical review team may decide that blood counts have not been performed and/or reported according to the protocol and are therefore inadequate for the evaluation of one/several hematological parameters in some patients.

Patients who have discontinued treatment because of toxicity will always be included in the safety analyses.

## **7.3 Evaluation of MGMT status**

Evaluation of MGMT is an integral part of the study design. MGMT status is divided into unmethylated (uMGMT) and methylated (mMGMT). Details of the evaluation can be found in chapter 11.

## **7.4 Evaluation of frailty using the G8 geriatric screening tool**

### **7.4.1 Background**

Older cancer patients have a much more heterogeneous general health status compared to young cancer patients. Some older patients are in perfect general health, while others are vulnerable or frail. Frailty is a well-known concept in geriatric medicine (Ref. 9). It is defined as a multi-factorial syndrome, resulting in a reduction of the physiological reserve and of the capability to resist stressful events (homeostatic capacity). Frailty is associated with an increased risk of unfavorable clinical events: disability, hospitalization, institutionalization, death. In oncology, the construct of frailty is as well used to describe patients with increased risk of treatment-associated morbidity and mortality. Presence of frailty can be detected by a so-called (Comprehensive) Geriatric Assessment (GA). Performance of GA is advised in older cancer patients by the International Society of Geriatric Oncology, SIOG (Ref. 55). GA is time consuming (takes about 30 minutes). Therefore, short geriatric screening tools such as the G8 have been developed as a short and easy to use measurement of general health status. The G8 score has been specifically developed in oncology, includes 8 items, takes a few minutes to complete, and can be completed by any health care worker (Ref. 2). The score ranges from 1 to 17. A score greater than 14 indicates that there is little risk that further GA reveals significant problems in the further assessed GA domains. The G8 was shown to strongly predict functional decline and overall survival (Ref. 26). G8 is by far the best studied geriatric screening tool in oncological patients, and also has better performance for detection of geriatric problems than other geriatric screening tools such as VES-13 (Ref. 11).

### **7.4.2 Assessments**

G8 will be measured in all patients aged 70 years and above at baseline. G8 has to be completed by the clinician, the nurse or the trained coder. This screening tool includes 7 items of the Mini Nutritional Assessment and the age of the patient. The English version of G8 is included as a protocol appendix.

### **7.4.3 Objective**

The inclusion of the G8 screening tool in EORTC trials will allow a uniform, easy and established approach of frailty at baseline. The G8 tool itself has been developed as a screening tool, and not a tool for follow-up.

The treating physician may decide which actions are needed based on the G8 result (e.g. further geriatric assessment in case of a G8 score of less or equal to 14; geriatric interventions if specific problems are detected within specific geriatric domains).

The assessment of frailty as defined by G8 in all patients aged 70 years and above entered in EORTC trials will allow interpretation of whether new treatment strategies have been tested in both fit and less fit patients which has importance for the generalizability of the study results.

## 8 Statistical considerations

### 8.1 Statistical design

#### 8.1.1 Sample size

For this study, we assumed that in the whole trial population the standard treatment plus marizomib presents with a superior OS efficacy compared to the standard treatment alone estimated by a hazard ratio (HR) equal to 0.74 (26% reduction of the hazard of death). This corresponds to a median OS of 16 months in the standard treatment alone compared to 21.6 months for standard treatment plus marizomib (Ref. 8; Ref. 17). We also assume that at the time of final analysis, the MGMT methylation status will be distributed 60% unmethylated, 30% methylated and 10% undetermined. We also hypothesized that the marizomib effect would be mainly present in the unmethylated MGMT subgroup where it would display a HR=0.70 (median OS of 13 months in the control arm and compared to 18.6 months for marizomib). The effect in the methylated MGMT subgroup would be HR>0.80 and in the undetermined cases which are assumed to be a balanced mixture of unmethylated and methylated MGMT cases the effect would be in the line with the overall population, i.e. HR=0.74.

Based on the network of institution, it should be possible to recruit 400 patients/year (150 patients in the first year, and then 400 patients per year).

For the primary endpoint OS, the formal statistical testing is based on comparisons between two treatment groups in both ITT population and unmethylated subgroup. We will use a graphical method (Ref. 5) to control overall Type 1 error at one-sided 2.5%. We have to recruit 750 patients to show the OS difference with 86% power (taking into account the interim analysis for futility) and overall one-sided 1.5% significance in the whole population and with 80.7% power and one sided 1% significance in the unmethylated MGMT subgroup (uMGMT). We will recruit these patients in about 30 months and will follow them up for about 19 months, the time necessary to observe the required 488 deaths (320 in uMGMT). We will perform the test in the ITT population and in the uMGMT subgroup simultaneously. If one of them is significant, we will attribute the assigned alpha to the other. At the final analysis, we will provide treatment effect estimates in the uMGMT and in the methylated MGMT (mMGMT) subgroups.

In order to avoid exposing too many patients to a possibly ineffective and/or toxic treatment, a non-binding futility analysis will be conducted on the whole population when about 88 deaths occur (18% information time). The interim analysis will be evaluated by an Independent Data Monitoring Committee (IDMC). The IDMC will recommend continuing the study or stopping the study for futility. If the observed hazard ratio (HR) is >1.12, the study may be considered to be futile.

We will analyze other endpoints at exploratory two-sided 5% significance.

#### 8.1.2 Randomization and stratifications

Patients will be centrally randomized (for practical details, see section on registration / randomization procedure). A minimization technique will be used for random treatment allocation. Pocock & Simon, 1975; Freedman & White, 1976). The minimization algorithm will be detailed in the SAP.

Stratification factors are:

- Institution,
- Age ( $\leq 55$ ,  $> 55$  years),

- Karnofsky performance status (70/80, 90/100),
- Extent of surgery (partial/biopsy, gross total).

## 8.2 Statistical analysis plan

### 8.2.1 Analysis populations

- Intention-to-treat population (ITT): All randomized patients will be analyzed in the arm they were allocated by randomization.
- Per protocol population (PP): All randomized patients who are eligible and have started their randomized treatment arm. Patients with major protocol deviations as defined in the medical review plan are also excluded from the PP population.
- Safety population (SP): All randomized patients who have started any treatment arm i.e. if a patient received treatment arm other than the patient's randomized treatment arm, then the patient will be assigned to the treatment arm that the patient actually received during the study in the analysis.
- Patients who did not start any treatment arm are excluded from PP and SP.
- Patients excluded from PP or SP will be reported in separate tables with the reason(s) of exclusion.
- Subgroups: The following subgroups will be defined: MGMT methylation status (uMGMT, mMGMT, unknown/missing), age ( $\leq 55$ ,  $> 55$  years), gender (male, female), Karnofsky performance status (70/80, 90/100), baseline steroid use (yes, no), extent of surgery (partial/biopsy, gross total).

A patient will be considered to be eligible if he/she did not have any deviation from the patient entry criteria listed in chapter 3 of the protocol. Potential eligibility problems will be assessed by the Clinical Research Physician at time of medical review.

### 8.2.2 Primary and secondary endpoints

#### 8.2.2.1 Primary endpoints

The primary endpoint is OS.

#### 8.2.2.2 Secondary endpoints

Secondary endpoints are:

PFS based on investigator assessment according to RANO 2010 criteria (Ref. 53).

ORR based on investigator assessment

CR/PR rate based on investigator assessment

DoR based on investigator assessment

Quality of Life according to the methodology described in chapter 10.

Mini Mental State Examination (MMSE).

Incidence of Adverse Event (AEs) in MedDRA terms graded according to NCI CTCAE Version 5.0; Laboratory results as measured by CTCAEs Version 5.0 criteria.

#### 8.2.2.3 Exploratory endpoints

Activity of the proteasome in the tumor tissue prior to treatment start and correlation with patient's outcome to assess prognostic and/or predictive value.

## 8.2.3 Statistical methods

### 8.2.3.1 Efficacy analyses

We will conduct all primary efficacy analyses in the intent-to-treat population.

In the primary analyses, differences between the treatment groups in OS will be assessed by a stratified LogRank test adjusted for the stratification factors assessed at randomization (except institution), testing the null hypothesis (H0):

- H0:  $HR_{MRZ\ arm/control} = 1$

Versus the alternative hypothesis (H1)

- H1:  $HR_{MRZ\ arm/control} < 1$

We consider this test as confirmatory and will perform it at a 1-sided significance level  $\alpha=0.015$  in the ITT population and  $\alpha=0.01$  in the uMGMT subgroup. If one of them is significant, the assigned alpha will be transferred to the other and the overall Type 1 error will be controlled at one-sided 2.5% by graphical method.

Kaplan-Meier survival curves (product-limit estimates) will be presented by treatment group, in the ITT population and by MGMT subgroup, together with a summary of associated statistics (median survival time, 6-, 12-, 18-, 24-month OS rate estimates and estimates for every 6 months thereafter as applicable) including the corresponding two-sided 95% confidence intervals (calculated by Greenwood formula's estimation of the standard deviation for rates and by Brookmeyer and Crowley technique for the median).

The hazard ratio (HR) (including two sided 97% and 95 % confidence interval in the ITT population and two sided 98% and 95 % confidence interval in the uMGMT subgroup) of the Marizomib group over the control group will be calculated by Cox's proportional hazards model stratified by the stratification factors assessed at randomization (except institution).

The primary analysis will take place after 488 deaths (320 uMGMT) deaths have occurred.

A re-randomization-test analysis will be performed to support the primary analysis in the ITT population and in uMGMT.

The re-randomization test will be performed as follows:

- The procedure will use 50,000 replications.
- Based on the value of their randomization stratification factors, for each replicate, subjects will be (virtually) re-assigned to treatments using the Medidata BALANCE minimization randomization algorithm in the order in which they were randomized into the trial.
- For each replicate the stratified log-rank test statistic adjusted by randomization stratification factors comparing the duration of overall survival will be computed.
- The re-randomization test p-values will be the fraction of replications where the log-rank p-values from the replicates are less than or equal to the corresponding p-values from the original analysis.

Robustness of the results will be established if the re-randomization test p-values are then found to be comparable to the corresponding p-values from the original analysis.

Secondary analyses of efficacy are supportive and will be analyzed in a non-confirmatory sense. Therefore no adjustments for multiplicity will be done. The following analyses will be performed:

The stratified LogRank test will be applied on the PFS time to test for differences between the 2 treatment groups. The Cox's proportional hazards model stratified by the stratification factors assessed at randomization (except

institution) will provide the hazard ratio (including 95 % confidence interval). Summary of associated statistics for each treatment arm (median PFS time, 6-, 12-, 18-, 24-month PFS rate estimates and estimates for every 6 months thereafter as applicable) will be displayed with 95 % confidence interval computed using the same methods as for OS, and the Kaplan-Meier curve for PFS will be presented.

For PFS and OS, Kaplan-Meier estimates will be calculated and unstratified Cox's proportional hazards model will be fit for each subgroup as defined in Section 8.2.1, in the ITT population only. Forest Plot will be displayed with a subgroup by treatment interaction test.

The best overall response will be presented in contingency table with frequencies and percentages. The objective response (ORR: CR/PR) and complete response rates will be reported with exact (binomial) two-sided 95% CI. The medians of objective (PR/CR) and complete (CR) response duration will be estimated from the Kaplan-Meier curves. The Brookmeyer and Crowley technique will provide two-sided 95% CI.

The evolution of MMSE over time will be interpreted taking into account the attrition as a result of patients assessed only until progression. All MMSE results will thus be conditional on the patients being otherwise free of progression. The distribution of the MMSE at each time point of evaluation will be described on the two treatment arms separately using means and their associated standard error (a graphical display will be considered). Median and range will also be provided. The proportion of patients with 'normal' and 'impaired' MMSE score at baseline and at key timepoints of evaluation (e.g. Baseline, at end of radiation therapy and then every 16 weeks, see table 6.4) will also be displayed. Longitudinal analysis might also be performed and detailed in the SAP.

All secondary analyses will be performed at 2-sided significance level  $\alpha=0.05$  for exploratory purpose.

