### **8.2.4 Pre-planned sensitivity or exploratory analyses**

If the percentage of patients excluded from PP is superior to 10% in at least one treatment arm, all efficacy analyses will be repeated in the PP population.

For both PFS and OS, the stratified LogRank test and the Cox's proportional hazards model will also be computed stratified by the stratification factors assessed at randomization (except institution) and MGMT methylation status.

Other exploratory analyses may be performed on the basis of subgroups of patients (see section 8.2.1), but results of these exploratory analyses may not serve as a basis for drawing conclusions concerning protocol efficacy.

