# 11 Translational research

## 11.1 Objective and projects description

Marizomib is a pan-proteasome inhibitor described in Section 1.1. Prior evidence is showing a trend regarding Marizomib therapeutic efficacy and baseline proteasomal activity in tumor cells (see section 1.1). Therefore, in this study, we plan to investigate the proteasomal activity in patients with sufficient amount of tissue available for these analyses. We have 2 objectives: firstly, we would like to confirm baseline proteasome activity and clinical response (PFS and OS), and secondly, we want to see if the proteasome activity is modulated by Marizomib in patients with tissue at baseline and at salvage surgery.

To perform proteasome activity measurement, frozen tumor tissue, at study entry and after salvage surgery should it occur, will be collected. Moreover, proteasomal activity will also be measured in the collected buffy coat and PBMC samples. The assessment of the proteasomal activity will be done by Eurofins (Breda, The Netherlands).

Proteasomal activity will be calculated based on the catalytic activity of the proteasome's three subunits and will be determined using a spectrofluorometric assay at a laboratory specified at a later date. However, at this stage, the exact substrates and precise mechanisms that govern marizomib activity in human tumors is not fully understood. So we plan to collect sufficient samples to facilitate exploratory research as our understanding improves. These analyses are of exploratory nature. Since the number of samples that are available for analysis cannot be predicted exactly, no statistics are provided.

Extracellular vesicles will be isolated from EDTA blood and stored at IBBL (Luxembourg, LU) for biomarker discovery.

FFPE Tumor tissue will be prospectively collected at IBBL (Integrated BioBank Luxembourg, LU) and send to HistoGeneX (Antwerp, BE) for central testing of the MGMT status. Since MGMT status will be used in the primary OS analysis to determine if there is a difference in treatment effect which is dependent on this variable, this initial tumor tissue is a MANDATORY requirement within this protocol. Subsequently, tissue samples will be stored at an EORTC central biobank (IBBL, Luxembourg; Rotterdam, NL or Zurich, CH). To allow for comprehensive immunohistochemical assessments of tumor tissue specimens, tissue microarrays (TMA) will be generated.

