intervals (calculated by Greenwood formula's estimation of the standard deviation for rates and by Brookmeyer and Crowley technique for the median).

Unstratified Cox's proportional hazards model will be fitted for each subgroup defined in section 11.5 in the ITT population only. Forest Plot will be displayed with a subgroup by treatment interaction test.

All secondary analyses will be performed at 2-sided significance level $\alpha=0.05$ for exploratory purpose.

The originally planned re-randomization test will not be performed as further to the review by the IDMC, there was no evidence that marizomib provides a benefit in overall survival and by consequence no significant result had to be validated with a re-randomization test.

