11.5. Subgroup Analyses

Overall survival and PFS will also be analyzed within the following subgroups:

- MGMT
- Age (≤ 55 , >55 years),

- Sex (male, female),
- Karnofsky performance status (70/80, 90/100),
- MMSE (≤ 27 , > 27),
- Baseline steroid use (yes, no),
- Extent of surgery (partial/biopsy, gross total).

Additional subgroup analyses based on other baseline disease characteristics might be performed as appropriate.

12. Safety Analysis

All safety analyses will be conducted using the SP.

The safety and tolerability will be followed from study treatment initiation through up to 30 days after the last administration of study treatment. The safety analyses will be reported for the whole study time and by treatment period for the safety analysis as defined below:

The concomitant period (TMZ/RT or TMZ/RT+MRZ) will start on the day of the first administration of radiation therapy and end 27 days after the day of the last administration of radiation therapy and before the start of adjuvant TMZ period whichever occurred first.

The adjuvant TMZ period (ie, when TMZ is administered alone or with MRZ) will start on the day of the first dose of adjuvant TMZ and end up to 27 days after the first day of administration of the last cycle of adjuvant TMZ

The maintenance MRZ period (ie, when MRZ is administered alone after discontinuation of TMZ) will start 28 days after the first day of administration of the last cycle of adjuvant TMZ and end up to 27 days after the first day of administration of the last cycle of maintenance MRZ.

The follow-up period (ie, when all treatments are discontinued) will start 28 days after the first day of administration of the last cycle of maintenance MRZ or adjuvant TMZ up to 30 days after the last treatment administration (MRZ or TMZ)

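### Subgroup hazard ratios drop the randomisation factors, and the MGMT interaction test is left unspecified with an uninformative third level: a small, cheap improvement

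*Protocol*

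**What the plan says.** **Main models.** Protocol 8.2.3.1 and SAP 11.2 and 11.3.1 estimate the main OS and PFS HRs by Cox models stratified by the randomisation factors except institution, that is age, KPS and extent of surgery. Protocol section 1 names younger age, better performance status and extent of resection as repeatedly shown prognostic factors.

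**Subgroup models.** In Protocol 8.2.3.1, for both endpoints, an "unstratified Cox's proportional hazards model will be fit for each subgroup as defined in Section 8.2.1, in the ITT population only". SAP 11.2 matches: "Unstratified Cox's proportional hazards model will be fitted for each subgroup defined in section 11.5 in the ITT population only". SAP 11.3.1 does the same for PFS. No reason is given for leaving the factors out.

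**Interaction test.** The only specification is that a "Forest Plot will be displayed with a subgroup by treatment interaction test". Neither document states the model, the degrees of freedom or the handling of unknown MGMT.

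**MGMT levels.** Protocol 8.2.1 defines "MGMT methylation status (uMGMT, mMGMT, unknown/missing") as the subgroup. SAP 11.5 opens with "Overall survival and PFS will also be analyzed within the following subgroups" and lists MGMT without levels; SAP 9.2 tabulates three categories at baseline.

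**uMGMT hazard ratio.** Protocol 8.2.3.1 gives a stratified Cox HR for uMGMT with 98% and 95% intervals. SAP 11.2 states the stratified HR for the ITT population only. SAP 5.4 promises estimates in the MGMT strata but names no model.

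**Role of MGMT.** Protocol 11.1 says MGMT will be used in the primary OS analysis "to determine if there is a difference in treatment effect which is dependent on this variable". Protocol 8.2.4 says of exploratory subgroup work that "results of these exploratory analyses may not serve as a basis for drawing conclusions concerning protocol efficacy".

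**The concern.** Protocol 8.1.1 expects the effect mainly in uMGMT tumours. A test within uMGMT shows whether there is an effect there; only a treatment-by-MGMT interaction addresses whether the effect differs by MGMT status. The forest-plot interaction test is the one planned analysis of that kind: the sensitivity analysis in Protocol 8.2.4 and SAP 11.4 uses MGMT as a stratum, with no interaction term.

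Three features deserve attention.

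- The subgroup HRs come from a different model than the main HRs. Omitting prognostic factors from a Cox model pulls the HR towards 1, so subgroup and overall HRs are not on the same footing.
- Under the SAP this may extend to uMGMT, one of the two populations in the confirmatory strategy: its p-value is stratified while its HR may not be.
- Protocol 8.1.1 assumes the undetermined group to be a balanced mixture with HR 0.74. If that group enters the interaction test, it uses a degree of freedom and adds nothing to the uMGMT-versus-mMGMT contrast.

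At stake is the quality of an exploratory answer, chiefly in the 488-death follow-up analysis. SAP 11.2 there tests OS separately in each MGMT category at two-sided 5%, which invites readers to take significance in one category and not another as evidence of a difference.

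**Working it through.** **Inputs from the documents** (Protocol 8.1.1, 8.3; SAP 2): ITT HR 0.74; uMGMT HR 0.70; mMGMT HR above 0.80; undetermined HR 0.74; 488 deaths, 320 of them in uMGMT; 1:1 allocation; futility boundary HR 1.12 at 88 deaths; 106 deaths at the 28 APR 2020 cutoff. Exploratory level: two-sided 5%.

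**Assumed:** the 168 deaths outside uMGMT split into 119 mMGMT and 49 unknown; at 106 deaths, 70/26/10.

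**1. The plan's own figures.** Power = Φ(√D/2 × |ln HR| − z).
- uMGMT: √320/2 × 0.3567 − 2.326 = 0.864, so 80.6% (stated 80.7%).
- ITT: √488/2 × 0.3011 − 2.170 = 1.156, so 87.6% before futility. With the HR > 1.12 rule at 88 deaths it is 86.1% (stated 86%).
- Futility stopping: 29.8% under no effect and 2.6% at HR 0.74 (stated about 30% and 2.6%).

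The figures reproduce, so the variance approximation 4/deaths is adequate here.

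**2. mMGMT HR implied by the design.** Weighting log HRs by deaths: (488 ln 0.74 − 320 ln 0.70 − 49 ln 0.74)/119 = −0.152, so HR 0.86. With 45 to 55 unknown deaths it ranges from 0.855 to 0.866.

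**3. Interaction power.**
- 1 df: the log ratio of HRs has variance 4/320 + 4/119 = 0.0461 (SE 0.215). At mMGMT HR 0.86 the log ratio is ln(0.86/0.70) = 0.206, so the non-centrality is (0.206/0.215)² = 0.92.
- 2 df: the non-centrality is the death-weighted spread of the three log HRs, also 0.92. The unknown group adds nothing, while the critical value rises from 3.84 to 5.99.

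| Deaths | mMGMT HR | 2 df, three levels | 1 df, uMGMT v mMGMT |
|---|---|---|---|
| 488 | 0.80 | 8.1% | 9.5% |
| 488 | 0.86 (design) | 12.6% | 16.0% |
| 488 | 1.00 | 30.0% | 38.3% |
| 488 | 1.20 | 61.3% | 70.9% |
| 106 | 0.86 | 6.5% | 7.3% |

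For 80% power on 1 df the ratio of HRs must be exp(2.80 × 0.215) = 1.83. The design implies about 1.14 (0.80/0.70) to 1.23 (0.86/0.70).

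**4. Adding stratification, by simulation** (750 patients, cut at 488 deaths).
- With an assumed prognostic HR of 1.5 for each of age, KPS and surgery, and 7,600–7,900 trials per scenario: at the design effect, 11.4% (2 df, unstratified), 14.3% (1 df, unstratified), 16.2% (1 df, stratified). With no mMGMT effect: 28.2%, 35.3%, 37.6%.
- With prognostic HRs of 1.0, 1.3 and 1.6 each and 800 trials per scenario (simulation error 1 to 2 points): at the design effect, stratifying moves 1-df power from 15.4% to 16.1%, 17.0% to 17.2% and 13.9% to 15.2%. The largest change is at mMGMT HR 1.2 with prognostic HRs of 1.6: 67.9% to 72.9%.

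**5. Attenuation.** A true uMGMT HR of 0.70 averages 0.714 unstratified with prognostic HRs of 1.5, and 0.728 with 1.8, against 0.700 stratified. The standard error of that log HR is √(4/320) = 0.11; ln(0.714/0.700) = 0.020.

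**The case against.** The strongest reply is that little depends on this. Secondary and subgroup analyses are labelled supportive and exploratory. The confirmatory uMGMT test is a stratified log-rank test and is untouched. The interim analysis has become the primary analysis, and the 488-death analysis is descriptive. With 106 deaths, eight age-by-KPS-by-surgery strata inside small subgroups would be very thin, so an unstratified model is defensible there. An unstratified HR is also a legitimate marginal quantity, and the shift of about 0.02 on the log scale is small against a standard error of 0.11. All of this stands; it sets the size of the point without removing it.

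Several stronger readings are tempting and unsupported:

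- **That every subgroup HR is unstratified.** Protocol 8.2.3.1 does give a stratified uMGMT HR; the gap is in SAP 11.2.
- **That the plan prescribes an unstratified 2-df interaction test.** The word unstratified describes the per-subgroup models. Three levels is the natural reading of Protocol 8.2.1, but it is an inference.
- **That the fix lifts power from 28% to 38%.** That scenario takes HR 1.00 in mMGMT and 0.84 in unknown. With 321/121/46 deaths it implies an ITT HR of exp[(321 ln 0.70 + 46 ln 0.84)/488] = 0.78, not the design's 0.74.
- **That attenuated subgroup HRs sit beside the stratified overall HR in one forest plot.** Neither document says the overall HR is printed there.
- **That Protocol 11.1 makes the interaction test part of the primary analysis.** Its sentence justifies mandatory tissue, and the uMGMT log-rank test is what sits in the primary analysis.

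**Conclusion.** The point holds as a low-cost improvement in specification and consistency. The subgroup models explicitly drop factors that the main models use. The SAP leaves the model for the uMGMT HR unclear where the Protocol is clear. The interaction test is unspecified, and its natural reading spends a degree of freedom on a group with no information about the contrast of interest.

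The size is modest. At 488 deaths and the design effects, the 1-df test gains about 3 points (11–13% to 14–16%) and stratifying adds about 0–2. The 1-df gain reaches about 7–8 points if marizomib has no effect in mMGMT, and about 10 if it does harm there (HR 1.2). At 106 deaths it is under 1 point. The number of deaths is the main limit, and the change does not alter that: the test stays near 16% at the design effect.

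A reader might infer that the primary conclusion is weakened. It is not, because the confirmatory tests do not use these models.

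These figures rest on assumptions outside the documents: the split of the 168 non-uMGMT deaths, exponential survival, the mMGMT control median and the prevalence of the factors in the simulations, and prognostic HRs between 1.0 and 1.8.

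**What to change.** Amend Protocol 8.2.3.1 and SAP 11.2, 11.3.1 and 11.5:

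1. Fit the subgroup and interaction Cox models adjusted for age, KPS and extent of surgery, omitting the factor that defines the subgroup. Use strata where deaths allow, and covariates where they are few, as at the 28 APR 2020 cutoff.
2. State the MGMT levels in SAP 11.5. Test the MGMT interaction on uMGMT versus mMGMT only (1 df), and show the unknown group's HR outside the test.
3. Restore in SAP 11.2 the stratified uMGMT HR of Protocol 8.2.3.1, so that estimate and log-rank test match.
4. State that the interaction test has low power, and align the sentence in Protocol 11.1 with the exploratory status of that test.

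Cost: a few lines of SAP text and code; the variables are already in the main model. The one downside is some loss of information in thin strata, which the covariate form avoids. The practical benefit falls mainly on the 488-death follow-up analysis.
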